# **Statistical Plan**

Pain of injection and pain of procedure are recorded on a categorical scale and compared using Student T-Tests. Percent of lesions requiring reinjection and percentage of lesions with "severe" bleeding were compared using Chi-square tests. To see if lesions size had any effect on these metrics, the lesions will be divided into < 1 mm, 1-5 mm, and > 5 mm, and analysis will be repeated on these groups.

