### **Clinical question**

Does bacteriostatic saline an adequate level of anesthesia compared to lidocaine with epinephrine while reducing pain associated with medication infusion in minor eyelid procedures.

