#### Intervention

- 1. 0.9% Bacteriostatic Saline
- 2. 2% Lidocaine + 1/100,000 Epinephrine

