#### **Outcome Measures**

Primary

- 1. Pain during injection (1-10)
- 2. Pain during procedure (1-10)

Secondary

- 1. Bleeding requiring >5 minutes of firm pressure or cautery
- 2. Need for additional anesthesia

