# **Study Protocol**

Prior to clinic day, patient list will be reviewed to identify potentially eligible patients. On the procedure day, eligible patients will be approached for participation following initial evaluation by attending physician. If patient amenable, patient will be consented for study. Photograph will be taken of the lesion directly in electronic medical record, and lesion circled using annotate function. Each lesion will be randomized separately using iPhone-based randomization application to either bacteriostatic saline or lidocaine with epinephrine. Fellow will be unblinded, attending physician blinded. Medication will be drawn up by fellow and handed to attending physician who will inject the medication. Immediately following injection, patient will be asked pain level on 0 to 10 scale, which was noted. Five minutes will be allowed to pass and then procedure will be commenced. If patient has more pain than acceptable to them, additional study agent will be injected and procedure re-started. If continued presence of pain, one more additional trial of the study agent will be allowed. If patient continues to have pain, medication will be defaulted to standard of care (lidocaine with epinephrine). Alternatively, if patient requests standard of care at any point, medication will be switched to this. Immediately following procedure, patient will be asked pain level on 0 to 10 scale, which was noted. Number of reinjections or need to default to standard of care will be noted. Bleeding level (Mild, moderate, or severe) will be noted. Mild is defined as not needing pressure to stop. Moderate is defined as needing five minutes or pressure to stop. Severe is defined as needing cautery or a pressure patch. Immediately following injection, patient will be asked pain level on 0 to 10 scale.

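### Procedure pain is tested only for a difference, so the plan has no rule for concluding that saline anesthesia is adequate

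*Combined protocol and SAP*

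**What the plan says.** The Clinical question has two halves. It asks whether saline gives "an adequate level of anesthesia compared to lidocaine with epinephrine while reducing pain associated with medication infusion". Outcome Measures makes injection pain and procedure pain both primary, and lists "Need for additional anesthesia" as secondary.

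The Statistical Plan gives the two pain outcomes the same analysis: "Pain of injection and pain of procedure are recorded on a categorical scale and compared using Student T-Tests". Reinjection and severe bleeding are compared by chi-square. No hypothesis, direction, margin, acceptable rate or confidence interval is stated for any of these.

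Under Study Protocol, a lesion with unacceptable pain may receive study agent up to two more times and is then defaulted to lidocaine with epinephrine. A second route is open throughout: "Alternatively, if patient requests standard of care at any point, medication will be switched to this". The procedure score comes after all of this: "Immediately following procedure, patient will be asked pain level on 0 to 10 scale, which was noted". Reinjections and defaults are recorded.

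**The concern.** The two halves of the question need different kinds of evidence. Less pain on injection is a superiority claim, and a difference test can support it. Adequacy against an active comparator asks whether saline is not worse by more than some tolerable amount. A t-test for a difference can show that saline is worse or that it is better. If it shows neither, it does not say how much worse saline might still be.

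So for one of two primary outcomes the plan has no criterion for a positive answer. A difference and its interval could be calculated later, but a margin chosen after the results are known would not be credible.

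A lesser concern is what the procedure score measures. It is taken after any rescue, and rescue in the saline arm can end in the comparator drug. If rescue lowers the score, the arms move together, in saline's favour.

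**Working it through.** There is no figure in the plan to reproduce: no SD, sample size, alpha, power or margin is given. The gap itself follows from the text. The arithmetic only shows its size, on assumed inputs.

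**Assumed inputs:** SD of procedure pain 2.5 points (range 2 to 3); two-sided 5%; equal arms of 20, 30, 50 or 100 lesions; lesions independent.

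**Step 1: precision.** Half-width of the 95% CI = t × SD × √(2/n). At n = 30: 2.00 × 2.5 × √(2/30) = 2.00 × 0.645 = 1.29.

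**Step 2: a true deficit that the test misses.** With a true 1-point deficit, the noncentrality is 1 / (SD × √(2/n)). At n = 30 this is 1 / 0.645 = 1.55, and the noncentral t distribution gives a non-significant result with probability 0.668.

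| Lesions per arm | 95% CI half-width (points) | P(non-significant), true 1-point deficit |
|---|---|---|
| 20 | 1.60 | 0.766 |
| 30 | 1.29 | 0.668 |
| 50 | 0.99 | 0.492 |
| 100 | 0.70 | 0.196 |

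At 30 per arm, the last column runs from 0.522 (SD 2) to 0.754 (SD 3).

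**Step 3: what a non-significant result leaves open.** If the observed difference falls just short of significance against saline, it nearly equals the half-width, so the upper limit is nearly twice that: about 3.2, 2.6, 2.0 and 1.4 points at the four sizes. Even with truly equal arms, at 30 per arm about 68% of non-significant trials (200,000 simulations) have an upper limit of 1 point or more, and about 12% have one of 2 points or more.

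**Step 4: the alternative measure of adequacy.** Suppose adequacy meant finishing without further anesthetic. Reinjection is then also tested only for a difference. With assumed true rates of 25% for saline and 10% for lidocaine, an uncorrected chi-square test (exact enumeration) is non-significant with probability 0.764, 0.665, 0.470 and 0.184 at the four sizes.

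**Step 5: the procedure score.** Study Protocol fixes its timing (straight after the procedure) and its scale (0 to 10). It does not say whether the patient is to report worst or overall pain. No section says whether reinjected or switched lesions are analysed as randomized, excluded or counted as failures. The likely direction of any rescue effect is toward no difference. Its amount depends on how often lesions are switched and what they then score, and the documents give neither.

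**The case against.** **The plan never says that non-significance means adequacy.** A reader might infer that it will be read that way, but no section says so. The gap is that no rule exists, which leaves the reading open until the data are seen.

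**Adequacy is covered by the need for additional anesthesia.** This stands in part. A pain-driven default comes only after further study agent, so those lesions already fall within the reinjection percentage. It would be wrong to infer that failures of saline go uncounted; only switches on request may escape. What is missing is an acceptable rate or margin, and separate reporting of defaults.

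**The score is named as pain during the procedure, so pain left at the end is an unnatural reading.** This also stands. The open questions are worst versus overall pain, and the handling of rescue. A reader might infer a definite bias from rescue, but its size cannot be estimated. Nor would scoring worst pain remove it: rescue cannot erase a peak already felt, but it can prevent a higher one later.

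**The numbers are assumed.** True, and the conclusion does not depend on them. A reader might also infer that, with equal agents, the planned test supports adequacy in only 2.5% of trials. That figure is just half of an alpha the documents do not state, and is not a measured loss.

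**Conclusion.** The main point holds and should be corrected before outcome data are examined. The Statistical Plan tests procedure pain, and reinjection, only for a difference, and the documents contain no margin, threshold or interval rule by which half of the stated question could be answered positively. On the assumptions above, at up to about 50 lesions per arm a true 1-point deficit goes undetected in roughly half of trials or more. These probabilities shift with the SD and treat lesions as independent, although each lesion is randomized separately and a patient may contribute several.

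The point about the pain score and rescue is secondary and less certain. The definition is incomplete and the likely direction favours saline, but no size can be given.

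**What to change.** 1. **Procedure pain.** Conclude that saline is adequate only if the upper limit of the two-sided 95% CI for mean(saline) minus mean(lidocaine), allowing for several lesions per patient, lies below a margin justified and fixed before outcome data are examined. If they have already been examined, label the margin post hoc. State that a non-significant difference is not evidence of adequacy.
2. **Injection pain.** Keep the superiority test. Claim a positive answer to the joint question only if both criteria are met.
3. **Score and population.** Analyse lesions as randomized and state which procedure pain is scored. Worst pain during the procedure would reduce dilution by rescue without removing it.
4. **Rescue.** Report the between-arm difference in reinjection with its 95% CI, and report defaults to standard of care separately. Add a supportive analysis that counts a switched saline lesion as a failure of saline.

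The rescue procedure itself is unchanged.

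**Cost.** Most of this is wording and an agreed margin, because scores, reinjections and defaults are already recorded. Asking for worst pain may need a change to the question put to patients, since it cannot be recovered from a score that did not ask for it.

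The real cost is that a small trial may be inconclusive on adequacy. With a true difference of 0 and 80% power, lesions per arm = 2 × (SD × 2.802 / margin)². At SD 2.5 and a 1-point margin this is 2 × (7.005)² = 98.1, so 99 (63 to 142 over SD 2 to 3). For 2 points it is 2 × (3.5025)² = 24.5, so 25 (16 to 36). Both margins are illustrations. The normal approximation is 1 to 2 lesions per arm too low, and several lesions per patient are not yet allowed for.

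### Chi-square is planned with no small-count rule and repeated in three lesion-size groups, where sparse, unbalanced tables would make its p-values unreliable

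*Combined protocol and SAP*

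**What the plan says.** The Statistical Plan gives the whole analysis of the two binary outcomes in one sentence: "Percent of lesions requiring reinjection and percentage of lesions with 'severe' bleeding were compared using Chi-square tests". To examine lesion size it adds that "the lesions will be divided into < 1 mm, 1-5 mm, and > 5 mm, and analysis will be repeated on these groups". On its natural reading this covers the binary outcomes as well as the pain scores.

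The events are defined under Study Protocol. For bleeding, "Severe is defined as needing cautery or a pressure patch". Reinjection depends on the patient's own tolerance: "If patient has more pain than acceptable to them, additional study agent will be injected and procedure re-started". Allocation is by lesion: "Each lesion will be randomized separately using iPhone-based randomization application to either bacteriostatic saline or lidocaine with epinephrine".

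The document names no exact test, continuity correction, expected-count rule, effect estimate or confidence interval. It also states no sample size, expected event rate, significance level, allocation ratio, blocking or stratification by size.

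**The concern.** The chi-square p-value is a large-sample approximation that becomes poor when expected counts are small. Splitting an unspecified total into three groups makes small counts more likely. Because allocation is not stated to be balanced within size groups, the arms inside a group can also be unequal.

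Three things are at stake:

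- In a sparse, unbalanced group, a result that looks significant could rest on a single lesion.
- The plan does not say whether a continuity correction applies, so two analysts could reach opposite conclusions from the same table.
- If a group has no events, the statistic cannot be computed and the plan has nothing to report in its place. One arm contains epinephrine and the other does not, so a table with few or no bleeding events could be misread as showing no difference.

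**Working it through.** **Inputs.** The test, the three size groups and per-lesion randomization come from the document. The document has no figure to reproduce on this point. Assumed here: two-sided 5% significance, simple 1:1 allocation, independent lesions, and a range of group sizes and event rates.

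**One event, in the smaller arm.** Let the arms have n1 and n2 lesions, N = n1 + n2, with one event in the n1 arm and none in the other.

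- Uncorrected Pearson: X² = N·n2 / [n1·(N−1)].
- Yates: X² = N·(n2 − N/2)² / [n1·n2·(N−1)].
- Fisher, two-sided, when n1 < n2: p = n1/N.

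For 2 v 8:

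- Pearson = 10×8/(2×9) = 4.44, p = 0.035.
- Yates = 10×(8−5)²/(2×8×9) = 0.625, p = 0.43.
- Fisher = 2/10 = 0.20.
- Smallest expected count = 1×2/10 = 0.2.

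| Table | Pearson p | Yates p | Fisher p |
|---|---|---|---|
| 1/1 v 0/4 | 0.025 | 0.40 | 0.20 |
| 1/2 v 0/8 | 0.035 | 0.43 | 0.20 |
| 1/3 v 0/12 | 0.038 | 0.44 | 0.20 |
| 1/5 v 0/25 | 0.023 | 0.36 | 0.17 |

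**When this happens.** X² exceeds 3.84 only if n2/n1 exceeds 3.84·(N−1)/N. That means a split of 3:1 in the smallest case (1 v 3), rising to about 3.8:1. With equal arms the formula reduces to N/(N−1). At 5 v 5 this is 10/9 = 1.11, p = 0.29, so one event in balanced arms never reaches 0.05.

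**Type I error given the split.** This is the sum of the binomial probabilities of all tables with Pearson p < 0.05 when both arms share one event rate. For 2 v 8 at a 5% rate, the single-event table alone contributes 2×0.05×0.95⁹ = 0.063.

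| Split | 5% rate | 10% rate |
|---|---|---|
| 2 v 8 | 6.5% | 8.6% |
| 3 v 12 | 8.0% | 8.7% |
| 5 v 25 | 7.1% | 5.1% |
| 10 v 10 | 0.1% | 0.9% |
| 15 v 15 | 0.5% | 2.5% |

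**How likely a single-event false signal is.** Under simple 1:1 allocation, a split of 4:1 or worse with both arms present occurs in 31% of 5-lesion groups, 11% of 10-lesion groups and 3.5% of 15-lesion groups. The event must also fall in the smaller arm. For 5 lesions this gives 0.3125×1/5 = 6.3%, given exactly one event. The corresponding figures are 2.0% at 10 lesions, 0.6% at 15 and 0.03% at 30. Multiplying by the chance of exactly one event at a 5% rate (for 5 lesions, 5×0.05×0.95⁴ = 0.204) gives about 1.3%, 0.6%, 0.2% and 0.01% per group.

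**The small-count condition does not need rare events.** With n lesions per arm, an expected count of 5 requires a pooled event rate of 5/n: 50% at n = 10, 33% at n = 15 and 17% at n = 30. Balanced tables can also show a gap between the tests: 3/5 v 0/5 gives 0.038 (Pearson) against 0.17 (Fisher), and 4/20 v 0/20 gives 0.035 against 0.11.

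**No events.** The Pearson denominator contains the total number of events, so it is zero. An interval still exists. For 0/15 v 0/15 the Wilson upper limit in each arm is 3.84/(15+3.84) = 0.204, so the 95% Newcombe interval for the risk difference is about −20 to +20 percentage points.

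**The case against.** A reader might infer that both outcomes are rare, that one event will readily produce a significant result, and that the planned test therefore inflates false positives in this trial. The document does not support that reading.

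- It gives no event rate. Reinjection follows whenever pain exceeds what the patient accepts and may be common. Severe bleeding includes any use of cautery or a pressure patch.
- The single-event result needs a split of about 3:1 to 4:1 or worse, the event in the smaller arm, and no continuity correction. The plan says only chi-square; under Yates the single-event results tabulated above disappear.
- The 31%, 11% and 3.5% figures are chances of the split alone. The chance of a false signal from one event is far smaller.
- Averaged over all 1:1 splits, uncorrected chi-square is not inflated, and in balanced sparse groups it is conservative.
- Fisher's test is itself conservative, so part of the gap between the p-values reflects Fisher rather than chi-square.
- These are secondary outcomes, and no decision rule is attached to the size groups.

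All of this stands and limits the point, but it does not remove it. Once an unbalanced split has occurred, the type I error given that split is what bears on the reported table, and at 2 v 8, 3 v 12 and 5 v 25 it is above 5%. The Yates argument also confirms the specification gap, because the same table gives 0.035 or 0.43 depending on a choice the plan leaves open.

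**Conclusion.** The point holds as a conditional weakness in specification. The plan relies on chi-square alone, repeats it in three groups of unknown size, and has no provision for small or zero counts. If a group is sparse and unbalanced, the uncorrected p-value can be several times too small (0.035 against 0.20 at 2 v 8), with a type I error given the split of about 5-9% at assumed rates of 5-10%. If a group is sparse and balanced, the test errs the other way and rarely rejects. A significant result resting on one event becomes unlikely at about 15 or more lesions per group.

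The size of the effect rests on assumed group sizes, event rates, 1:1 allocation and a 5% two-sided level, none of which the document states. It is worth correcting because the change is cheap. It does not threaten the primary pain comparisons.

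**What to change.** In the Statistical Plan, state that:

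- any 2×2 table with an expected count below 5, overall or within a size group, is tested with one pre-named exact test (for example Boschloo) instead of chi-square, with its two-sided convention fixed in advance;
- where chi-square is kept, the plan says whether a continuity correction applies;
- every table, including those with no events, is reported as counts with a risk difference and a 95% score-type interval, either Newcombe or Miettinen-Nurminen, with the choice named.

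The convention matters: Boschloo p-values for 4/30 v 0/30 of 0.053 and 0.07 are both obtainable, depending on how the two-sided test is formed.

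The cost is a sentence or two and standard software. Some p-values will become less favourable. An exact test does not restore power in sparse groups; the interval is what shows how much difference remains possible. None of these methods accounts for several lesions from one patient, which is a separate point.

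### Bleeding is graded in three ordered levels, but only severe versus not is tested, so a rise in moderate bleeding in the arm without epinephrine is not assessed

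*Combined protocol and SAP*

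**What the plan says.** The Study Protocol section has an ordered three-level record: "Bleeding level (Mild, moderate, or severe) will be noted". The levels are then defined:

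- Mild: "Mild is defined as not needing pressure to stop".
- Moderate: "Moderate is defined as needing five minutes or pressure to stop".
- Severe: "Severe is defined as needing cautery or a pressure patch".

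The Statistical Plan compares only the top level between arms: "percentage of lesions with 'severe' bleeding were compared using Chi-square tests". It then repeats its analyses by lesion size: "the lesions will be divided into < 1 mm, 1-5 mm, and > 5 mm, and analysis will be repeated on these groups". No analysis of the mild or moderate grades is described, overall or by size.

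Outcome Measures lists bleeding as a secondary outcome that is already binary, with a different threshold: "Bleeding requiring >5 minutes of firm pressure or cautery".

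Under Intervention, one arm is "0.9% Bacteriostatic Saline" and the other is lidocaine with epinephrine.

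**The concern.** The planned test counts a lesion that needed no pressure and a lesion graded moderate as the same result. If saline moved many lesions from mild to moderate and few to severe, the comparison would show almost nothing, although the data to see the shift had been collected.

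The arms differ in epinephrine, so a difference in bleeding is a natural question for this trial. If saline proves less painful to inject, a non-significant severe-only result could be taken to mean that it carries no cost in bleeding. The plan as written could not support that reading for moderate bleeding. The permitted switch to lidocaine with epinephrine can dilute a bleeding difference further, whichever test is used.

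**Working it through.** **No figure to reproduce.** The documents give no sample size, significance level, power or bleeding rates. Everything below is assumed: two-sided 5% level, equal allocation, independent lesions, and a range of grade mixes written mild/moderate/severe in percent.

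**Step 1. Information kept by severe versus not.** If one odds ratio applies at both cuts (proportional odds), the information relative to the three-grade analysis is

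[1 − s³ − (1 − s)³] / [1 − Σpᵢ³],

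where pᵢ is the grade mix averaged over the arms and s is the severe share.

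- 80/15/5: (1 − 0.000125 − 0.857375) / (1 − 0.512 − 0.003375 − 0.000125) = 0.1425 / 0.4845 = 29% kept.
- 85/5/10: (1 − 0.001 − 0.729) / (1 − 0.614125 − 0.000125 − 0.001) = 0.27 / 0.38475 = 70% kept.

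| Averaged mix | Kept | Lost |
|---|---|---|
| 90/8/2 | 22% | 78% |
| 80/15/5 | 29% | 71% |
| 60/30/10 | 36% | 64% |
| 90/5/5 | 53% | 47% |
| 60/20/20 | 63% | 37% |
| 85/5/10 | 70% | 30% |
| 45/10/45 | 91% | 9% |

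The loss passes one half where severe is uncommon and moderate clearly more common. It stays below one half where severe is about as common as moderate, or more so.

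**Step 2. Lesions per arm for 80% power, odds ratio 3.** Take 80/15/5 in the epinephrine arm. The severe share under saline is 3 × 0.05 / (0.95 + 0.15) = 13.6%. The moderate-or-severe share is 3 × 0.20 / (0.80 + 0.60) = 42.9%.

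- Severe only, 5% against 13.6%: [1.96 √(2 × 0.0932 × 0.9068) + 0.842 √(0.0475 + 0.1178)]² / 0.0864² gives 177.
- Ordered: 6 (1.96 + 0.842)² / [(ln 3)² × (1 − Σpᵢ³)] = 47.1 / (1.207 × 0.666), which gives 59.

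Other mixes in the epinephrine arm, severe-only against ordered: 100 against 47 (60/30/10), 100 against 69 (85/5/10) and 64 against 45 (50/30/20). The ratio runs from 3.0 (177/59) to 1.4 (64/45) over these mixes.

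**Step 3. Simulated power.** This used an uncorrected chi-square on severe versus not and a tie-corrected Wilcoxon on three grades, with 40,000 simulated trials per row.

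| Epinephrine arm | Saline arm | 50 per arm: severe-only / ordered | 100 per arm: severe-only / ordered |
|---|---|---|---|
| 75/20/5 | odds ratio 2.5 | 22% / 59% | 41% / 87% |
| 60/20/20 | odds ratio 2.5 | 54% / 68% | 83% / 93% |
| 85/5/10 | odds ratio 2.5 | 38% / 47% | 64% / 77% |
| 80/15/5 | 50/45/5 | 4% / 85% | 4% / 99% |
| 75/20/5 | 65/20/15 | 39% / 25% | 68% / 45% |
| 60/30/10 | 60/10/30 | 73% / 13% | 96% / 20% |

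With no difference between arms, the ordered test rejected in about 5% of trials for the three mixes in the first three rows, so its gain is not bought with false positives. That check also assumes independent lesions.

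**Step 4. The categories side by side.** A lesion held under firm pressure for longer than five minutes, without cautery or a patch, meets the listed outcome but not the definition of severe. A lesion that needs a pressure patch and no cautery is severe, but the listed outcome does not mention a patch. The definition of moderate can be read as a duration or as any pressure at all. The tested category is therefore not the listed outcome.

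**The case against.** A binary bleeding outcome is what Outcome Measures lists, so testing a threshold is not in itself a departure from the plan. That is right. It does not rescue the severe cut, because the threshold tested is not the one listed.

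A reader might infer that the severe-only test throws away most of the bleeding information. The documents do not support this as a general statement. They give no grade rates and nowhere say that severe is the rarest grade. Proportional odds also favours an ordered test. With 85/5/10 and an odds ratio of 2.5, the gap at 50 per arm is only 38% against 47%.

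A reader might also infer that an ordered test should replace the severe comparison. The last two rows of the simulation argue against that. When severe bleeding triples from 5% to 15% and moderate stays at 20%, the planned test is the more powerful. Replacement would trade one blind spot for another.

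Two further points stand. An ordered test gives weight to the moderate grade, whose definition is the least clear, so the wording has to be settled first. And each lesion is randomized separately, so one patient can contribute several, which any added test must allow for.

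**Conclusion.** The point holds in a limited form. Three ordered grades are recorded, one cut is tested, and a rise confined to moderate bleeding would be missed almost entirely: about 4% power under the assumed shift. That much follows from the plan's own text.

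The general size of the loss cannot be fixed from the documents. Over the mixes in the table of information kept it runs from 9% to 78% under proportional odds, and the advantage reverses when the effect falls mainly on the severe grade. All of the power figures rest on assumed rates and independent lesions.

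It might be inferred that bleeding is the trial's main foreseeable harm. The documents do not say so. They list it as a secondary outcome, do not rank harms and make no claim that the arms are equivalent in bleeding. The point needs only that bleeding is a listed outcome and that the arms differ in epinephrine. It is an inexpensive improvement to a secondary analysis and does not touch the primary comparisons.

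**What to change.** In the Statistical Plan:

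1. Keep the severe-versus-not comparison, and report it as a risk difference with 95% CI.
2. Add a table of mild, moderate and severe counts and percentages by arm.
3. Add one prespecified ordered comparison of the three grades: a proportional-odds model giving an odds ratio with 95% CI, with standard errors that allow for several lesions per patient. A tie-corrected Wilcoxon test could supply the p-value, with the same allowance for clustering.
4. In the same edit, reconcile the bleeding categories in Outcome Measures, Study Protocol and Statistical Plan, including the wording of moderate, so that the outcome listed, the grade recorded and the category tested agree.

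The first three items cost a sentence or two and a table, and use grades that are already to be recorded. Reconciling the categories may change how a few lesions are graded. The statistical cost is one more test on a secondary outcome. The ordered test is less sensitive to a shift confined mainly to the severe grade, which is why the severe comparison stays beside it.

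### The lesion-size analysis repeats the arm comparison within three size bins, so it gives no test or interval for the size question it poses

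*Combined protocol and SAP*

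**What the plan says.** The Statistical Plan names two base analyses. For the pain scores: "Pain of injection and pain of procedure are recorded on a categorical scale and compared using Student T-Tests". The percentages of lesions needing reinjection and of lesions with severe bleeding "were compared using Chi-square tests". With two agents under Intervention and each lesion randomized to one of them under Study Protocol, these are arm-versus-arm comparisons.

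The size analysis has its aim and its method in one sentence: "To see if lesions size had any effect on these metrics, the lesions will be divided into < 1 mm, 1-5 mm" and above 5 mm, after which "analysis will be repeated on these groups".

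No section names a size term in a model, a trend test, a contrast between bins or an arm-by-size interaction. Size does not appear under Clinical question or Outcome Measures. The documents give no sample size, significance level, power or expected bin counts. A patient may contribute more than one lesion (Participants, Study Protocol), but the Statistical Plan does not say how this is handled.

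**The concern.** The aim can mean two things: that size changes the metric itself, or that size changes the difference between the arms. Each is a comparison between bins. The stated method compares arms inside each bin and stops there, so neither question receives an estimate with an interval or a test.

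What is at stake is the reading of the results. The planned output is a set of significance tests per bin, with no rule for combining them. A reader may see one bin below 0.05 and another above it and conclude that size matters. That pattern is common when the true arm difference is the same at every size, because each bin holds only part of the data.

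**Working it through.** **1. What the method produces.** Four metrics (two pain scores, reinjection, severe bleeding) times three bins gives 4 × 3 = 12 arm-versus-arm comparisons and no between-bin comparison. An effect of size on a metric needs a contrast of bin means or percentages. A dependence of the arm difference on size needs a contrast of the bin-specific arm differences. Neither is specified. This step uses no assumed number.

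**2. How often the bins would disagree on significance under a uniform arm effect.** The plan has no figure to reproduce, so all inputs here are assumptions: two-sided 5%, independent lesions, normal approximation, same true arm effect in every bin.

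- Overall shift at 80% power: 1.960 + 0.842 = 2.802 standard errors.
- Bin shift = overall shift × √(bin share). Equal thirds: 2.802 × √(1/3) = 1.618.
- Power within a bin: P(Z > 1.960 − 1.618) = 0.366.
- P(disagree) = 1 − P(all significant) − P(none significant) = 1 − 0.366³ − 0.634³ = 1 − 0.049 − 0.255 = 0.696.

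The same formula elsewhere:

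| Bin shares | 30% overall power | 50% | 80% | 90% | 99% |
|---|---|---|---|---|---|
| Equal thirds | 34% | 49% | 70% | 75% | 63% |
| 10/60/30 | 35% | 50% | 73% | 81% | 82% |
| Smallest bin empty, 60/40 | 29% | 41% | 51% | 48.5% | 27% |

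With no arm effect and three bins: 1 − 0.05³ − 0.95³ = 14%. With equal bins the rate peaks at 75% near 92% overall power and falls to 15% at 99.999%.

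**3. Comparison with an interaction test.** Simulation of 20,000 trials with SD 2, 30 lesions per arm per bin and a uniform arm difference of 0.84 (80% overall power): the bins disagree in 69% of trials, while a 2 df interaction test on the same data is significant in 5%.

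**4. A true size effect with no arm effect.** Same SD and bin sizes, mean pain rising by a fixed step per bin:

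| Step (points per bin) | No bin significant in the arm tests | Size term significant |
|---|---|---|
| 0 | 85% | 5% |
| 0.5 | 86% | 68% |
| 1 | 86% | 99.9% |
| 2 | 86% | 100% |

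The arm-test p-values do not respond to the size effect, as expected by construction. The bin means would show the gradient, but without a test or interval.

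**5. Precision of an interaction.** With arm effects of 0, 1 and 2 times the average in equal thirds, the noncentrality is (1/3 + 0 + 1/3) × 2.802² = 5.23. On 2 df this gives 52% power at 80% overall power (28%, 66% and 89% at 50%, 90% and 99%). With effects in ratio 0:1:2 and a 10/60/30 split, the noncentrality is 1.96 and power 22% at 80% overall power. The standard error of a difference between two equal-third bins is √6 = 2.45 times that of the overall arm difference.

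**6. Several lesions per patient.** Suppose every patient has two lesions in the same bin with intraclass correlation 0.5, and size has no effect. The design effect for a size contrast is 1 + (2 − 1) × 0.5 = 1.5. An unadjusted 2 df test then rejects with probability P(χ² > 5.99/1.5) = exp(−1.997) = 0.136, or about 14% instead of 5%.

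**The case against.** Repeating an analysis in subgroups and describing the results is ordinary exploratory practice, and the stated aim does not promise a formal test. A reader might infer that the plan will declare a size effect from the pattern of significant bins. The documents do not say so, and the disagreement rates in step 2 describe only that unstated rule. They also run from 14% to 82% across the scenarios, so they show that the rule can mislead and do not predict a rate for this trial. This stands.

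A reader might also infer from step 4 that the repeated analysis says nothing about size. That is too strong: it holds for the arm-test p-values only. Bin means and percentages carry information on size. What is missing is inference.

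The wording could also mean that the size groups are compared with each other. A chi-square test handles three groups, so reinjection and severe bleeding would then have a between-bin test. But the text does not say this, a single Student t-test does not compare three groups, and the analysis being repeated is the arm comparison. Part of the defect is therefore ambiguity, which the plan can remove.

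Finally, the interaction test will often be inconclusive. That is true, but low precision is a reason to show an interval. Separate tests in smaller groups are imprecise too and do not address the question.

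**Conclusion.** The point holds as a defect of an exploratory analysis. On its natural reading, the stated method does not test or estimate with an interval either meaning of the stated size question. That conclusion rests on the text alone.

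The size of the risk is illustrative and conditional on bins being read by significance. The figures of about 70% disagreement and about 5% false positives for an interaction test assume two-sided 5%, independent lesions, equal bins and 80% overall power, none of which the documents state.

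It would be wrong to infer that the main results are compromised. The overall comparison of arms does not use the bins, and no listed outcome depends on them. The change is worth making because the plan itself poses the question and a suitable method costs little.

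**What to change.** For each metric, use a linear model for pain and a logistic model for reinjection and severe bleeding:

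1. Fit arm + size category. Report the size contrasts with 95% CIs, as the answer to whether size affects the metric.
2. Add arm × size. Report the interaction contrasts with 95% CIs, as the answer to whether the arm difference depends on size.
3. Show bin-specific arm differences with 95% CIs as descriptive.
4. State the method for several lesions in one patient, for example patient-clustered standard errors, GEE or a patient random effect. It has to be written here because the Statistical Plan has none to refer to.
5. Merge an empty or very sparse bin with its neighbour. If a metric has too few events for a stable model, report it by bin descriptively only.
6. Label the whole size analysis exploratory and unadjusted for multiplicity. State that no size effect will be inferred from which bins are significant, and that a non-significant interaction will not be read as no dependence on size.

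Cost: a few sentences in the plan and two short models per metric, using the size categories already planned and no new data. The downside is the low precision of the interaction shown in step 5 of the working, so its intervals will often be wide.
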